10.4 Causality Assessment

The following “binary” decision choice will be used by the Investigator to describe the causality assessment:

- Reasonable possibility of a relatedness
- No reasonable possibility of relatedness.

The expression “reasonable possibility of relatedness” is meant to convey, in general, that there are facts (evidence), or arguments meant to suggest a causal relationship.

The Investigator will be asked to consider the following before reaching a decision on causality assessment:

- Time relationship between study drug intake and event’s onset
- Dechallenge (did the event abate after stopping drug?)
- Rechallenge (did the event reappear after reintroduction?)
- Medical history
- Study treatment(s)
- Mechanism of action of the study drug
- Class effects
- Other treatments-concomitant or previous
- Withdrawal of study treatment
- Lack of efficacy/worsening of existing condition
- Erroneous treatment with study medication (or concomitant)
- Protocol related process.

10.5 Action Taken with the Study Drug due to an Adverse Event

- Dose not changed
- Drug permanently withdrawn
- Drug temporarily interrupted
- Dose reduced
- Dose rate reduced
- Not applicable.

10.6 Other Actions Taken

- Specific therapy/medication
- Concomitant procedure.

Clinical Study Code No.: CLI-10067AA1-01	Version No.: 6.0
EUDRACT No.: 2022-001079-15	Date: 06 July 2023

10.7 Outcome

Each AE must be rated by choosing among:

- Recovered/resolved
- Recovering/resolving
- Not recovered/not resolved
- Recovered with sequelae/resolved with sequelae
- Fatal
- Unknown.

10.8 Recording Adverse Events

All AEs occurring during the course of the study must be documented in the AE page of the eCRF. Moreover, if the AE is serious, the SAE Form must also be completed.

It is responsibility of the Investigator to collect all AEs (both serious and non-serious) derived by spontaneous, unsolicited reports of subjects, by observation, and by routine open questionings.

The recording period for AEs is the period starting from the informed consent signature until the subject's study participation ends.

Clinically significant abnormalities detected at screening visit not due to a pre-existing condition or clinically significant changes at the following visits in the medical opinion of the Investigator must be reported as AEs in the eCRF.

If a clinically significant abnormal laboratory finding or other abnormal assessment meets the definition of an AE, then the AE eCRF page must be completed, as appropriate. A diagnosis, if known, or clinical signs and symptoms if diagnosis is unknown, rather than the clinically significant abnormal laboratory finding, should be reported on AE eCRF page. If no diagnosis is known and clinical signs and symptoms are not present, then the abnormal finding should be recorded.

For pharmacovigilance purposes, all SAEs should be followed-up in order to elucidate as completely and practically as possible their nature and/or causality until resolution of all queries, clinical recovery is complete, laboratory results have returned to normal, stable condition is reached or until the subject is lost to follow-up. Follow-up may therefore continue after the subject has left the study. In this case, the follow-up will continue with no timelines for related SAEs, while for unrelated SAEs the type and extent of follow-up undertaken will be determined for each individual case and will depend upon the nature (e.g., events with poor prognosis or which do not resolve), severity, and medical significance of the event.

Clinical Study Code No.: CLI-10067AA1-01	Version No.: 6.0
EUDRACT No.: 2022-001079-15	Date: 06 July 2023

10.9 Reporting Serious Adverse Events to Chiesi

The Investigator must report all SAEs to the Fortrea Safety Contact listed below within 24 hours of awareness. The information must be sent by providing the completed paper SAE form. At a later date, the Fortrea Safety Contact will report all information to Chiesi Global Pharmacovigilance, the Clinical Project Manager, and the Clinical Research Physician.

Safety Contact	Fax No.	E-mail
Fortrea Safety Contact	[contact]	[contact]
Chiesi Safety Contact	[name]	[contact]

- Reporting of SAEs from the Investigator site is from the time of subject's signature of informed consent and until the subject's study participation ends. After this date, even if no active monitoring of subjects is required, SAEs occurring to a subject should be reported if the Investigator becomes aware of them.
- Up to the closure of the site, SAE reports should be reported to the Fortrea Safety Contact. New SAEs occurring after the site is closed should be reported directly to the Chiesi Safety Contact.

10.10 Reporting Serious Adverse Events to Regulatory Authorities/Ethics Committee

All SUSARs, which occur with the investigational medicinal products within or outside the concerned clinical study, if required, will be reported in compliance with the timelines and standards for reporting SUSARs. The Medicines and Healthcare products Regulatory Agency (MHRA) will be informed through MHRA Individual Case Safety Report (ICSR) Submission portal, while other relevant Regulatory Authorities in accordance with local requirements. The ECs and the Investigators will be informed by Council for International Organisations of Medical Sciences I form or by periodic line listings produced by Chiesi Global Pharmacovigilance.

With regard to regulations in force for Pharmacovigilance, the Investigators must fulfil their obligation according to the law in force in their countries.

10.11 General Notes

- In case of death, a comprehensive narrative report of the case should be prepared by the Investigator and sent to the Fortrea Safety Contact together with the SAE form, retaining a copy on site.
- If an autopsy is performed, copy of autopsy report should be actively sought by the Investigator and sent to the Fortrea Safety Contact as soon as available, retaining a copy on site.

Clinical Study Code No.: CLI-10067AA1-01	Version No.: 6.0
EUDRACT No.: 2022-001079-15	Date: 06 July 2023

- All documents provided by the Investigator or site staff to the Fortrea Safety Contact must be carefully checked for respect of confidentiality. All personal subject's data must be redacted.
- In case of pregnancy discovered after treatment with study drug, the subject may remain on the study until completion for safety monitoring purposes, if these are considered safe by the Investigator. The subject will be asked (with a separate consent) to be followed with due diligence until the outcome of the pregnancy is known and till the age of one year of the child to detect any congenital anomaly or birth defect. The pregnancy must be reported by the Investigator within 24 hours by fax/e-mail to the Fortrea Safety Contact using the paper Pregnancy Report Form. The Fortrea Safety Contact will inform Chiesi of the pregnancy within 1 working day of being notified.
- The first 2 pages of the Pregnancy Report Form should be completed by the Investigator with all the available information and sent to the Fortrea Safety Contact. Information collected in specific sections relative to the pregnancy will be recorded in the form only upon signature of the specific ICF by the subject/subject's partner. The third page will be completed as soon as the Investigator has knowledge of the pregnancy outcome, together with a follow-up of the first 2 pages, if necessary (e.g., an update in the medications received during pregnancy by the mother). If it meets the criteria for immediate classification of a SAE (e.g., spontaneous or therapeutic abortion, stillbirth, neonatal death, congenital anomaly, birth defect) the Investigator should follow the procedure for reporting SAEs.
- If it is the partner, rather than the subject, who is found to be pregnant, the same procedure regarding pregnancy reporting is to be followed and the Pregnancy Report Form should be completed.
- If the pregnancy is discovered before taking any dose of study drug, the pregnancy does not need to be reported; it is only required that the subject is immediately withdrawn from the study.
- Any ADR occurring with any marketed non-investigational medicinal product and/or concomitant medication during the study must be reported by the Investigator to his/her concerned Health Authority and/or to the relevant Marketing Authorisation Holders of the involved medicinal products according to the applicable laws. Additionally, also conditions of use outside the marketing authorisation of the medicinal products (i.e., off-label, overdose, misuse, abuse, and medication errors) or from occupational exposure, as well as cases of suspected drug interaction, pregnancy, breast-feeding exposure and lack of efficacy should be reported.

11. DATA MANAGEMENT

An eCRF will be filled in by the Investigator and/or his/her representative designee.

Front-end edit checks will run at the time of data collection and back-end edit checks will be used by the Data Manager to check for discrepancies and to ensure consistency and completeness of the data.

Clinical Study Code No.: CLI-10067AA1-01	Version No.: 6.0
EUDRACT No.: 2022-001079-15	Date: 06 July 2023

Medical history, AEs, and concomitant procedures will be coded using the MedDRA dictionary; medications will be coded using the World Health Organisation Drug dictionary and Anatomical Therapeutic Chemical classification.

External data (PK, immunogenicity, immediate hypersensitivity reactions systemic markers, spirometry, diffusing capacity, plasma TG2 samples) will be processed centrally, sent to the designated Contract Research Organisation, and reconciled with the corresponding information recorded in the eCRF.

Access to electronic systems used for data collection will be granted to the study personnel only after appropriate training.

After the completion of data collection and cleaning, a review meeting will be held to determine the occurrence of any protocol violation and to define the subject populations for the analysis. Once the database has been declared to be complete and accurate, it will be locked, the randomisation codes will be opened, and the planned statistical analysis will be performed.

If the database is unlocked after the initial lock, the process must be carefully controlled and documented; updates to the study data must be authorised by Chiesi.

At the study conclusion, a complete copy of the study data will be created for archival purposes at Chiesi. The Investigators will receive copies of the subject data for retention at the investigational sites.

12. STATISTICAL METHODS

12.1 Sample Size

This study is designed to explore the safety and tolerability of CHF10067 for the first time in subjects affected by IPF, while exposing a minimum number of subjects; therefore, no formal power calculation was performed.

A sample size of 24 subjects (8 subjects per cohort; 6 treated with CHF10067 and 2 with placebo) is deemed adequate to assess safety and tolerability of CHF10067. In each cohort, a minimum of 2 subjects are required to be not receiving antifibrotic treatment (including subjects with previous use of antifibrotic treatment that has been stopped for at least 2 weeks prior to screening).

12.2 Analysis Sets

Safety set: all randomised subjects who receive a dose of study treatment, including partial dose.

PK set: all subjects from the safety population excluding subjects without any valid PK measurement or with important protocol deviations significantly affecting PK, for example, use of non-permitted medications. Exact definition of important protocol deviations significantly affecting PK will be discussed by the clinical team and described in a specific

Clinical Study Code No.: CLI-10067AA1-01	Version No.: 6.0
EUDRACT No.: 2022-001079-15	Date: 06 July 2023

document before bioanalytical data are disclosed. Subjects will not be excluded on the basis of statistical analysis or for PK reasons, except in the cases defined in the European Medicine Agency guideline [24].

After unblinding, subjects will not be excluded on the basis of statistical or for PK reasons, except in the case of:

- non-zero baseline concentration $> 5\%$ of C_{\max}
- AUC_{0-t} lower than 5% of the reference medicinal product geometric mean of AUC_{0-t} (calculated without inclusion of data from the outlying subject)
- below the limit of quantification concentration at all timepoints.

Pharmacokinetic variables will be analysed in the PK set. The safety set will be used in the analysis of all safety variables. In case of deviation between randomised treatment and treatment actually received, the treatment actually received will be used (i.e., an as-treated analysis will be performed).

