6.2.2.1 Dose escalation

The doses will be administered according to an escalation scheme designed to ensure sufficient safety conditions for subjects. In each cohort, subjects will be divided into 2 sub-groups, with each sub-group being dosed at least 24 hours apart. The first sub-group will comprise 2 subjects, with 1 subject receiving CHF10067 and 1 subject receiving placebo. The second sub-group will comprise 6 subjects, with 5 subjects receiving CHF10067 and 1 subject receiving placebo.

Clinical Study Code No.: CLI-10067AA1-01	Version No.: 6.0
EUDRACT No.: 2022-001079-15	Date: 06 July 2023

Continuation to dose the remaining 6 subjects will be evaluated by at least the Medical Monitor and Sponsor Clinical Research Physician based on the safety data (e.g., AE profile) provided by the Investigator(s) where the first sub-group have been dosed. The procedure for communication and initiation of dosing the remaining subjects within each cohort will be clearly detailed in a separate charter.

The decision to escalate to the next dose will be made by the Safety Advisory Committee when safety data until Day 14 have been collected for all subjects at the previous dose level. Pharmacokinetic and immunogenicity data will also be included in the safety evaluation for dose escalation (if available) but are not mandatory to escalate to the next dose.

The Safety Advisory Committee will comprise at least the Coordinating Investigator, Medical Monitor, Sponsor's representatives (these may also include Key Opinion Leaders), and site Investigators identified from some of the enrolling sites. The presence of all site-Investigators is not mandatory. This committee will be governed by a separate charter.

A blinded interim safety report, summarising results from all available safety assessments for each subject, as specified above, will be sent by the Investigator(s) and appropriately blinded PK and immunogenicity data (if available) will be sent by the appropriate parties to the Sponsor and Safety Advisory Committee prior to the start of each successive group. Unblinding during the interim review may occur in certain situations, if necessary to take an informed decision, and will be clearly detailed in a separate charter.

A Safety Advisory Committee meeting will occur prior to each dose escalation. In particular, any clinically significant results will be discussed before dose escalation continues.

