7.2.1.2 Determination of CHF10067

Blood samples (1 sample = 3.5 mL) for determination of serum CHF10067 will be collected at the following timepoints: pre-dose (within 75 minutes from start of infusion), at the end of infusion, 2, 4, 8, and 20 hours after the end of infusion and 5, 7, 14, 28, 56, and 84 days post-dose. The selected timepoints are based on the results obtained after single dose in healthy subjects. Timepoints may be adjusted during the study if the PK profile in IPF patients is significantly different than healthy subjects. In that case, decisions will be taken by the Safety Advisory Committee and appropriately documented. The total number of timepoints is not expected to be modified.

The time deviation window for PK sampling will be:

- \pm 5 minutes for timepoints \leq 2 hours
- \pm 15 minutes for timepoints $>$ 2 hours and \leq 8 hours
- \pm 1 hour for the timepoint of 20 hours
- \pm 1 day for Days 5 and 7
- \pm 2 days for Days 14, 28, 56, and 84.

The processing, storage and shipment of samples are detailed in the Laboratory Manual document.

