- The adjusted correlation coefficient of the linear regression should be ≥ 0.85 , otherwise the $t_{1/2}$ as well as the derived parameters (AUC_{inf} , CL and Vz) are not reliably estimated and will not be reported (presented as “NR” (not reported) in the tables).

Criteria for AUC_{inf} estimation

- When for a profile the $AUC_{extrapolated} / AUC_{0-\infty} > 20\%$, this AUC_{inf} as well as the derived parameters (CL and Vz) will be excluded from the statistical analyses.

All PK parameters will be estimated, if feasible, and presented in the TLFs, unless specified differently (e.g., unreliable $t_{1/2}$). PK parameters that cannot be estimated will be specified in the Data Review Report (DRR) (*prior* to database lock and disclosure of the bioanalytical data) and/or PK DRR (*after* database lock and disclosure of the bioanalytical data). PK data that is excluded from PK analysis will be discussed in the DRR and/or PK DRR, and marked in the relevant tables, accompanied with a footnote.

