6. GENERAL METHODOLOGY

6.1 ANALYSIS SETS

6.1.1 *Analysis sets*

The following analysis sets will be considered in the statistical analysis:

Enrolled Set (ENR): subjects who *signed an informed consent* to participate in this study

Randomised Set (RND): subjects who were *randomised* into this study

Safety Set (SAF): all randomised subjects who receive a dose of study treatment, including partial dose

PK Set: all subjects from the safety set excluding subjects without any valid PK measurement or with important protocol deviations significantly affecting PK, for example, use of non-permitted medications.

Notes:

- Having signed an informed consent is defined as having a complete informed consent signature date in the database.
- Randomised is defined as having a randomisation date in the database or any information to confirm randomisation.
- Having received at least one dose of study treatment is defined as having an exposure date or any information confirming exposure.
- Exact definition of important protocol deviations significantly affecting PK evaluations will be discussed by the Chiesi team during the Data Review Meeting (DRM) and described in the DRR and/or PK DRR. The PK set will be defined in the DRR and/or PK DRR. See section 6.1.3.1 for further details. Subjects will not be excluded on the basis of statistical analysis or for PK reasons, except in the cases defined in the European Medicine Agency guideline on the Investigation of Bioequivalence

Unless stated otherwise, the SAF will be used for the general characteristics, demographics and baseline characteristics, immunogenicity and safety tables and figures and the RND will be used for the general characteristics and safety listings. In addition, the PK set will be used for demographics and baseline characteristics tables, if different than the SAF. PK set will be used for the PK tables, listings and figures.

6.1.2 *As planned versus as actual analysis*

For the safety, immunogenicity, other variables (TG2) and PK analyses the actual treatment of the subject will be considered. The general characteristics analyses will be by planned treatment. In the listings the actual treatment will be presented.

6.1.3 *Exclusion of data from the statistical analyses*

The important/non-important protocol deviation definitions are defined in the Protocol Deviation Criteria List and will be used to identify cases that will be

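### The SAP lets the deviations that affect PK be defined after bioanalytical disclosure, which protocol 12.2 rules out, and SAP 7.1 does not list the change

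*Protocol*

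**What the plan says.** **Protocol 12.2 (Analysis Sets)** removes from the PK set subjects with no valid PK measurement or with important deviations significantly affecting PK, and gives non-permitted medication as the example. The clinical team is to agree the exact definition and record it in a specific "document before bioanalytical data are disclosed". After unblinding, exclusion for statistical or PK reasons is barred except in three listed cases.

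**Protocol 11 (Data Management)** places the population decisions after data cleaning and before lock and code opening: "a review meeting will be held to determine the occurrence of any protocol violation and to define the subject populations for the analysis".

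**SAP 6.1.1** sends the same definition to the data review meeting, to be described in either or both of the two reports, and adds: "The PK set will be defined in the DRR and/or PK DRR". SAP 6.1.3 uses the same two-report wording for decisions to exclude subjects or values.

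**SAP 2.1.2** dates the two reports. The DRR precedes database lock and disclosure. The other is described as "PK DRR (*after* database lock and disclosure of the bioanalytical data".

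**SAP 7.1**, which lists changes to the planned analysis, does not mention this one.

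**The concern.** The protocol's timing rule stops anyone from deciding that a deviation matters for PK because of the concentration it came with. The SAP keeps the rule's subject but adds a second place to apply it, and that place comes after concentrations are known. Whether a course of a prohibited drug significantly affects PK is a judgement. Made blind to exposure it is harmless; made with the profile in view it allows selection on the result.

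The result at stake is the PK summary by dose and the power-model slope. SAP 2.1.3 reads the slope as showing no evidence of departure from proportionality when its 90% interval contains 1. Protocol 1.2 says that the PK data will help to set doses for later studies. Each dose has only six active subjects.

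**Working it through.** **1. Timing, side by side**

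| Decision | Protocol | SAP |
|---|---|---|
| Definition of PK-affecting deviations | Before disclosure (12.2) | DRR (before) or PK DRR (after) (6.1.1, 2.1.2) |
| Deviation-based exclusion of subjects or values | Subject populations defined at review meeting before lock (11) | DRR (before) or PK DRR (after) (6.1.3) |
| Three named exclusions: pre-dose above 5% of Cmax, AUC0-t below 5% of the geometric mean, all values BLQ | After unblinding (12.2) | After disclosure (6.1.3.1) |

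The third row agrees. In the first two rows, the DRR route agrees with the protocol and the PK DRR route does not.

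**2. Do other rules close the gap?**

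- The bar on post-disclosure exclusion (protocol 12.2, SAP 6.1.3.1) covers statistical and PK reasons. It says nothing about exclusion for a deviation.
- The sampling rules in SAP 6.1.3.1 fix the handling of many missed, mistimed or unreportable samples. They do not reach non-permitted medication, the protocol's own example.
- The Protocol Deviation Criteria List (SAP 6.1.3) separates important from non-important deviations. Which important ones significantly affect PK is the later step that SAP 6.1.1 leaves to the two reports. The SAP gives no date for the list.

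The discretion is narrowed but not closed.

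**3. Size of one exclusion (illustration)**

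The plan gives no figure to reproduce: no power calculation was made and no PK variability is stated. The design input is six active subjects at each of 1000, 2000 and 3000 mg, 18 in all. Between-subject CV is assumed to be 20, 30 or 40%, with log-normal errors.

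- Log-scale SD: s = √ln(1 + CV²) = 0.198, 0.294, 0.385.
- Natural-log doses are 6.908, 7.601 and 8.006, with mean 7.505. The deviations are −0.597, 0.096 and 0.501.
- Sxx = 6 × (0.597² + 0.096² + 0.501²) ≈ 3.70.
- SE of slope = s/√3.70 = s/1.924 = 0.103, 0.153, 0.200.

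*Dropping the highest of six at 3000 mg* (true slope 1, 20,000 simulated trials per CV, averages):

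| Assumed CV | Geometric mean ratio at 3000 mg | Change in slope | In SE units |
|---|---|---|---|
| 20% | 0.951 | −0.039 | 0.38 |
| 30% | 0.93 | −0.058 | 0.38 |
| 40% | 0.907 | −0.076 | 0.38 |

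*Dropping one subject lying 2 SD below the line, all others on it.* The shift is 2s × |deviation|/Sxx. At 3000 mg this is 2s × 0.501/3.70, or +0.054, +0.079, +0.104. At 1000 mg it is 2s × 0.597/3.70, or −0.064, −0.095, −0.124. In SE units these are about 0.5 and 0.6.

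*Outer bound.* Suppose the true slope were 0.7 and any one of the 18 could be dropped with exposures known. The chance that the 90% interval contains 1 would rise from 13% to 25% at CV 20%, from 40% to 60% at CV 30%, and from 58% to 75% at CV 40% (4,000 simulations each).

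None of these calculations models a deviation. A real case needs an influential subject who also has an arguable important deviation. The figures show the most that one exclusion might do, not how often it would happen.

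**The case against.** **The compliant route is available and probably intended.** Protocol 11 and SAP 2.1.2 both place the review meeting and the DRR before lock and disclosure. A definition written there meets protocol 12.2. This stands, and it limits the point to the PK DRR alternative. A reader might infer that leaving the definition to the final data review is itself too late; the documents do not support that.

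**The PK DRR is needed.** Three exclusions can be applied only once concentrations are known, so final membership cannot be closed earlier. This also stands. Removing the PK DRR from the definition of the PK set altogether would contradict protocol 12.2 and SAP 6.1.3.1.

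**The stronger reading.** A reader might infer that exposures are already disclosed at each escalation, because "appropriately blinded PK and immunogenicity data (if available) will be sent by the appropriate parties to the Sponsor and Safety Advisory Committee", and because "Timepoints may be adjusted during the study if the PK profile in IPF patients is significantly different than healthy subjects" (protocol 7.2.1.2). The documents do not establish this. The data are blinded, are sent only if available, and "are not mandatory to escalate to the next dose". Protocol 6.6 keeps the Sponsor's clinical team blinded without direct access to the randomisation list. Whether anyone deciding PK-set membership could link a concentration to a subject may depend on a committee charter that is not among the documents. What remains is that disclosure is undefined in a trial where PK may circulate during conduct.

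**Transparency and stakes.** Exclusions are listed with reasons (SAP 2.1.4, Listing 16.2.5.3), so a late decision could be seen, though not undone. PK is a secondary objective and the safety analysis uses the safety set.

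**Conclusion.** The conflict is real and narrow. Protocol 12.2 requires the definition before disclosure; SAP 6.1.1 and 6.1.3, read with SAP 2.1.2, also permit it afterwards; SAP 7.1 does not say so. The existing bars and sampling rules do not cover deviation-based exclusion in general.

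The possible effect is moderate: about 0.4 SE of the slope on average for the highest of six at 3000 mg, or 0.5 to 0.6 SE for a subject 2 SD from the line. In absolute terms both depend on the assumed CVs, and both assume that the exclusion could be justified by a deviation. The documents do not show that such a choice has been or will be made. The change is worth making because it restores, at almost no cost, a protection that the protocol already promises.

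**What to change.** 1. **SAP 6.1.1 and 6.1.3.** State that three things are fixed before bioanalytical disclosure, in the dated DRR or the Protocol Deviation Criteria List: the list of PK-affecting deviations, the handling of each (sample or subject), and every deviation-based exclusion from the PK set. Delete *and/or PK DRR* for those decisions.
2. **Keep the PK DRR** for the three post-disclosure exclusions in protocol 12.2 and SAP 6.1.3.1, for the PK-parameter criteria in SAP 2.1.2, and for recording the final PK set once those rules have been applied.
3. **Define disclosure.** Say whether blinded PK shared at escalation, or used to review sampling times, counts. If subject-level PK reached anyone who decides membership, declare it in SAP 7.1.

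Cost: a few sentences in the SAP and a date on a document the process already produces. No data, subjects or analyses are added.
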